SPECIFIC AIM 2: Physiological impact of rTMS therapy in PCD

Aim 2a: We will determine the physiological effects of 1-Hz rTMS therapy when combined with BoNT injections in PCD. We will record the time course of effects on cerebellar inhibition (CBI) at T1, T2 and T3 follow-ups by MAGSTIM system. We hypothesize that compared to T1, CBI will be reduced and reach physiological levels at T2 follow-up. CBI will continue to remain at physiological levels at T3 follow-up though to a lesser extent.

Aim 2b: We will determine if the physiological effects of 1-Hz rTMS therapy as reflected in CBI, will correlate with the clinical scoring of PCD symptoms. We hypothesize that the change in CBI measure at T2 and T3 follow-ups will show positive correlation with the improvement in PCD symptoms at these time points.

4/20/2015

STUDY DESIGN: Subjects receiving BoNT therapy for a diagnosis of PCD will be enrolled. Diagnosis of PCD will be established in accordance with the Consensus Statement of the Movement Disorders Society.²⁷ In this two year study, we plan to recruit 20 subjects with PCD in the age range 21-80 years. Subjects followed at our center regularly fill out a self-reported form to document the duration of benefits they perceive with BoNT therapy. We will enroll subjects who report benefits lasting 10 weeks or less only (suboptimal benefits with standard care). Specifically, our inclusion criteria are: 1) Diagnosis of PCD according to the Consensus Statement of the Movement Disorders Society; 2) Report benefits of BoNT lasting 10 weeks or less only. We will exclude subjects with 1) pregnancy; 2) active seizure disorder 3) presence of a metallic body such as pacemaker, implants, metal rods and hearing aid. We will also identify subjects who meet inclusion/exclusion criteria from the IRB approved database (#416-2002). These subjects have consented to be contacted for future research. We will enroll 10 healthy age and sex-matched controls for normative electrophysiological data. Controls will be recruited through fliers placed across the campus. Specifically, our inclusion criteria are: 1) There is no history of any neurological disorders; 2) Neurological exams are unremarkable. We will exclude subjects with 1) pregnancy; 2) any neurological disorders 3) presence of a metallic body such as pacemaker, implants, metal rods and hearing aid.

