Outcome measures. The clinical outcome will be measured with Toronto Western Spasmodic Torticollis Rating Scale (TWSTRS). The TWSTRS is a widely accepted composite rating scale for PCD with subscales for clinical severity, functional disability, and associated pain. Studies evaluating the clinimetric properties of TWSTRS have demonstrated substantial reliability, validity, and responsiveness to change following therapeutic intervention. It is the most commonly employed outcome measure in PCD trials and has practical applicability in a clinical setting. Also, we will administer the Craniocervical Dystonia Questionnaire Description for quality of life assessment. The Craniocervical Dystonia Questionnaire (CDQ-24) is a patient-rated health related quality of life (HR-QoL) measure for craniocervical Dystonia on 5 HR-QoL domains. It is composed of 24 items, forming 5 subscales: stigma, emotional well-being, pain, activities of daily living, and social/ family life. Items are rated on a 5-point scale.²³ Each item consists of five statements representing increasing severity of impairment, scored from 0 to 4. Subjects will be instructed to indicate how they have felt during the past two weeks because of dystonia by selecting one of the five statements for each item. Subjects will also rate their symptoms before and after stimulation using a 7-point nominal scale: 1) excellent, 2) very good, 3) good, 4) average, 5) slightly worse than usual, 6) bad or 7) very bad.

We will record videos of subjects at T1, and possibly at T2 and T3 time points which will be scored by two independent blinded raters (excluding control patients). We will obtain IRB approval to consent subjects in order to obtain videos of all subjects (excluding control subjects). The physiological outcome will be measured with TMS (CBI measure). We will also obtain MRI scan before and after rTMS therapy.

Brain Structure Measures: We will be using the research dedicated 3T Phillips or 3T Siemens MRI scanners in the McKnight Brain Institute to obtain diffusion tensor imaging, T1 weighted, and T2 weighted images. ²¹ We will be using the 32 channel head coil (Phillips) or 64 channel head coil (Siemens) for data acquisition.

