Data Safety Monitoring Plan

The principal investigator monitors the patient safety and data collection of each study visit. If she feels there is possible harm to subject safety or the possibility of, any harm due to something new that was learned during the study, she will convene a multi-disciplinary committee of at least 2 health professionals to perform a thorough review of the study details.

Regulatory Approval, Statistics, Time Line

The study will be approved by the University of Florida Institutional Review Board, and all subjects will provide informed consent. The study is highly feasible given the large number of PCD subjects seen at UF and the considerable expertise. Statistical analyses will be performed using commercially available statistical software (SPSS, version 19.0; SPSS, Inc., Chicago, Illinois). We aim to enroll 20 subjects for this pilot study, and 10 control subjects. For Aim1 and 2a, we will conduct a mixed model analysis using time and stimulation arm as repeated factors adjusted for baseline values, and subjects as the random factor. The model will include 2 factors: treatment (2 levels: real vs sham) and time (3 levels: T1, T1, and T3). The 2-tailed significance level will be set at 0.05 For Aim 2b, we will use Spearman correlation test to determine the relation between the change in CBI at T2 compared to that at T1 and change in CBI at T3 compared to that at T1. With an expected difference of 30% in TWSTRS scores at 10 weeks between the two arms (real and sham rTMS), a standard deviation of 20%, type I error of 5% and power of 80%, the necessary sample size for each group is ten completers.

TIME AND EVENTS TABLE

Description	Screenin g	rTM S V1	rTM S V2	rTMS V3	rTMS V4	rTMS V5	10 wk FU*	12wk FU*
Consent	Х							
Neurological Exam	Х							
Med History	Х							
Inclusion/Excl.	Х							
Botox Injection (SOC)	X							
Randomization	x							
MRI		Х				Х		
rTMS (real/shame)		Х	Х	Х	Х	Х		
Determine Threshold	X							
Videotape		Х				Х	х	Х
Blinded Rater Eval		Х				Х	х	Х
Urine pregnancy	x							
CDQ 24	Х					Х	Х	Х
Clinical Assessments								
TWSTRS		Х				Х	Х	X

Physiological Tests						
CBI measured with TMS	X			Х	Х	Х

*optional

References:

1. Fahn S (Ed): Movement disorders 2. London: Buttersworth; 1987.

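### The Aim 2b test correlates one CBI change with another and contains no clinical measure, so it cannot answer Aim 2b and leans positive because both changes share the T1 value.

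*Combined protocol and SAP*

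**What the plan says.** Specific Aim 2, Aim 2b, sets out to learn whether the physiological effects of rTMS, as seen in CBI, "will correlate with the clinical scoring of PCD symptoms". Its hypothesis reads: "the change in CBI measure at T2 and T3 follow-ups will show positive correlation with the improvement in PCD symptoms at these time points". The aim therefore pairs a physiological change with a clinical change, at each of two follow-ups.

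Regulatory Approval, Statistics, Time Line gives the only analysis for this aim, a Spearman test of "the relation between the change in CBI at T2 compared to that at T1 and change in CBI at T3 compared to that", where the reference for the second change is again the T1 value. No clinical variable appears in that sentence, and no other section describes an analysis linking CBI to a clinical score. The sentence does not say whether the real and sham arms are pooled.

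The same paragraph fixes the error rate: "The 2-tailed significance level will be set at 0.05". Outcome measures names the TWSTRS as the clinical outcome and adds the CDQ-24 and a 7-point self-rating. Study Design plans 20 patients, 10 per arm. The Time and Events Table marks the 10- and 12-week follow-ups as optional.

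**The concern.** There are two faults in the sentence as written, and one omission that would matter even with the right variables.

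1. **Wrong pair.** The test asks whether patients whose CBI moved by T2 also had CBI moved at T3. That concerns the persistence of a physiological change. It says nothing about symptoms, so the stated aim has no valid test.
2. **Shared baseline.** Both differences subtract the same T1 value. A T1 reading that is high by chance makes both changes low, and the reverse. The two changes therefore tend to correlate positively even when CBI is pure measurement noise.
3. **Arm handling.** The plan expects real rTMS to move both CBI and TWSTRS. If both do shift in the real arm, pooling the arms gives a correlation between them even when no patient-level relation exists within either arm.

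At stake is a likely significant result, filed under Aim 2b, that could be taken as support for the proposed mechanism without any evidence linking physiology to symptoms.

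**Working it through.** **The plan's own figure.** The only sample size statement is for Aim 1: a 30% difference in TWSTRS with SD 20%, two-sided 5%, 80% power, ten completers per group. The standardised difference is 30/20 = 1.5. A two-sample t-test needs 8.06, so 9 per group, and ten gives power 0.887. The stated ten is adequate for Aim 1 under those inputs. No figure is given for Aim 2b.

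**Expected correlation of the planned pair.** Let v1, v2, v3 be the CBI variances at T1, T2, T3, and c12, c13, c23 the covariances. Then

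corr(T2−T1, T3−T1) = (v1 − c12 − c13 + c23) / √[(v1 + v2 − 2c12)(v1 + v3 − 2c13)].

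The documents give none of these quantities, so the following are assumptions:

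- Equal variances v and equal covariances c: (v − c)/(2v − 2c) = 0.50, whatever the between-visit correlation.
- AR(1) with correlation 0.8: (1 − 0.8 − 0.64 + 0.8)/√(0.4 × 0.72) = 0.36/0.537 = 0.67. With 0.5 the value is 0.61.
- Independent visits, v2 = v3 = 1: v1/(v1 + 1). This is 0.20 for v1 = 0.25, 0.33 for v1 = 0.5 and 0.67 for v1 = 2.

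The expected value turns negative only if c12 + c13 exceeds v1 + c23.

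**How often the planned test is significant with no effect.** Simulation with 20,000 trials per setting, normal data, no treatment effect and no clinical link, Spearman test at two-sided 0.05:

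| CBI assumption | Expected Pearson | Mean Spearman, n=20 | p<0.05, n=20 | p<0.05, n=10 |
|---|---|---|---|---|
| Equal variance, equal correlation (0, 0.5, 0.8) | 0.50 | 0.46 | 56–57% | 27–28% |
| AR(1) 0.5 | 0.61 | 0.57 | 79% | 43% |
| AR(1) 0.8 | 0.67 | 0.63 | 89% | 53% |
| T1 variance one quarter, independent | 0.20 | 0.18 | 13% | 9% |
| T1 variance half, independent | 0.33 | 0.30 | 27% | 14% |
| T1 variance double, independent | 0.67 | 0.62 | 88% | 52% |

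In the equal-variance case about 98% of trials of 20 give a positive coefficient.

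**The intended pair.** Replacing the second CBI change with an unrelated clinical change gives mean rho about 0 and significance in 4.9–5.5% of trials at n=20, and 5.2–5.7% at n=10. The artefact disappears.

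**Pooling the arms with the intended pair.** Two arms of 10, no within-arm relation, arm shifts in SD units for the two variables:

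- 1.5 and 1.5: mean rho 0.38, significant in about 39%.
- 1.0 and 1.0: mean rho 0.20, about 14%.
- 1.5 and 0.5: about 10%.
- 0.5 and 0.5, or 1.5 and 0: about 5%.

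The 1.5 for TWSTRS is the plan's own 30/20. Every CBI shift is an assumption. Adjusting the ranks for arm returns mean rho to about 0 and the rejection rate to about 5%.

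**Power of the corrected test.** Fisher z approximation, power = Φ(atanh(ρ)·√(n−3) − 1.96). With n = 20, power is 42%, 62%, 82% and 95% for ρ = 0.4, 0.5, 0.6 and 0.7. These ρ values are assumed.

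**The case against.** The best defence is that the sentence is a drafting slip. It lists exactly the two CBI changes that the hypothesis needs, T2 against T1 and T3 against T1, and could simply have lost the clinical variable. The same paragraph has another slip, giving the three time levels as T1, T1 and T3. If the intended pair were analysed, the shared-baseline artefact would never arise. That reading is plausible, but it does not rescue the plan. The statistics paragraph is the operative text, and an analyst who departs from it must choose the clinical measure, the pairing of time points, the arm handling and the coding of sign without prespecification.

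It can also be said that a reader would see that a CBI-only correlation does not bear on symptoms, so misreading is not certain. That is fair. The certain harm is that Aim 2b has no usable test; the misleading positive is a further risk.

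The sizes depend on assumptions, and 57% is one point in a range. That stands, as does the point that 39% for pooled arms is towards the unfavourable end of the shifts tried and presumes that a within-arm relation is what Aim 2b seeks. The plan is silent on pooling and does not prescribe it, so this part is secondary.

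Finally, Aim 2b is a mechanistic aim in a 20-patient pilot, and the primary goal, Aims 1 and 2a and the sample size are untouched. This limits the reach of the fault but does not make the sentence correct.

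**Conclusion.** The concern holds. That the Aim 2b test omits the clinical variable follows from the text alone and needs no assumption: as written, it cannot answer the aim. That it tends to be positive follows from the shared T1 value. The expected correlation is 0.50, with about 57% significance at 20 patients, if CBI variances and between-visit correlations are equal; the rate ranged from 13% to 89% across the other settings examined and never fell to 5%. Twenty pairs is an upper bound, because the T2 and T3 visits are optional. The effect of pooling arms is real but depends on an unstated CBI effect. This must be corrected before analysis, because a named specific aim has no valid test.

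**What to change.** Replace the Aim 2b sentence in Regulatory Approval, Statistics, Time Line with wording to this effect:

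- Spearman correlation between change in CBI from T1 to T2 and change in TWSTRS from T1 to T2, and separately between the two changes from T1 to T3.
- Each computed as a partial rank correlation adjusted for treatment arm.
- The TWSTRS score to be used (total or a named subscale) stated in advance.
- The sign convention stated, so that a positive coefficient means that movement of CBI in the hypothesised direction goes with a fall in TWSTRS. Aim 2a expects CBI to be reduced and improvement is also a fall in score, so the meaning of positive depends on the coding.

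The cost is one or two sentences. CBI and TWSTRS are already planned at these time points, so no new procedure is needed. Adjusting for arm costs one degree of freedom: at an assumed ρ of 0.5, power is Φ(0.549 × √16 − 1.96) = 59%, against 62% unadjusted. Restricting the test to the real-rTMS arm would also remove the arm effect but halves the sample: Φ(0.549 × √7 − 1.96) = 31%. The adjusted version is preferable. Missed optional visits will lower these figures, so the number of pairs should be reported with each coefficient.

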Eligible subjects will be invited to an introductory session. We will obtain IRB approved informed consent. Subjects will be explained in detail about the procedures outlined for the study. Subjects will have a detailed medical history and neurological examination using the NINDS Common Data Elements. Subjects will be randomized to receive BoNT therapy combined with real or sham rTMS (1:1, 10 subjects in each arm). At our center, PCD subjects are scheduled for BoNT injections approximately every 12 weeks. rTMS therapy will be administered in the period around 2-8 weeks before or after the BoNT injections. Although the physician administering TMS will be aware of the status of the subject in terms of real TMS versus sham-TMS, this physician will play no role in any of the outcome measures, and will not be present during any of the outcome measure assessments. Similarly, the investigator who performs the outcome measures will not be present during any of the TMS sessions, and therefore will remain blinded to the status of the patients with respect to real rTMS versus sham rTMS.

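### Randomisation is scheduled at Screening, apparently weeks before the first TWSTRS and rTMS session; assigning the arm at rTMS V1 would cheaply protect the small randomised set

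*Combined protocol and SAP*

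**What the plan says.** **Order of events.** The Time and Events Table places consent, eligibility, the BoNT injection, motor threshold and "Randomization" in the Screening column. The first TWSTRS, videotape, blinded rating and MRI are at rTMS V1, together with the first stimulation session.

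**Timing.** Study Design states that "rTMS therapy will be administered in the period around 2-8 weeks before or after the BoNT injections". Specific Aim 1 puts T1 at about six weeks from the injection, or at the start of rTMS.

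**Numbers.** Study Design randomises 10 patients per arm. The statistics section (Regulatory Approval, Statistics, Time Line) says that "the necessary sample size for each group is ten completers". The mixed model for Aims 1 and 2a includes a baseline adjustment. No loss allowance, replacement rule, analysis set or missing-data rule is given.

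**Blinding.** Study Design says that "the physician administering TMS will be aware of the status of the subject in terms of real TMS versus sham-TMS". That physician is kept out of outcome assessment. The outcome assessor and the video raters are blinded. The plan does not say how allocation is concealed, who holds the list, when the physician learns the arm, or who books V1.

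**The concern.** Nothing scheduled between Screening and V1 depends on the arm. Threshold is set at Screening, and the sham arm goes through the same procedure to locate the stimulation site. Early randomisation therefore gains nothing, and it has two possible costs.

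1. A patient who leaves before V1 counts as randomised but has no T1 TWSTRS, and so drops out of the primary model as a post-randomisation exclusion. With the number randomised equal to the number of completers required, there is no slack on paper.
2. An allocation that exists while the V1 date is still open could in principle affect that date. The date matters because the introduction puts average BoNT benefit at about 9.5 weeks and the central hypothesis puts its peak at about 4-6 weeks. The T1 score, and hence the T1-to-T2 change, depends on where in that course T1 falls.

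**Working it through.** **1. Length of the gap.** The documents state no interval from randomisation to V1. It has to be inferred:
- Table: randomisation and BoNT share the Screening column, and rTMS V1 follows.
- Study Design: rTMS is about 2-8 weeks from BoNT, in either direction.
- If rTMS follows BoNT and the Screening items fall close together, the gap is about 2-8 weeks (about 6 at the nominal T1).
- If rTMS precedes BoNT, the table does not describe the sequence and the gap is undefined.

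**2. The plan's sample size.** Inputs, all from the statistics section: "With an expected difference of 30% in TWSTRS scores at 10 weeks between the two arms"; "a standard deviation of 20" per cent; "type I error of 5% and power of 80" per cent; "The 2-tailed significance level will be set at 0.05". The standardised difference is d = 30/20 = 1.5.
- Normal approximation: n = 2(1.96 + 0.842)²/1.5² = 6.98, so 7 per arm.
- Two-sided t-test (noncentral t): n = 8.06, so 9 per arm.
- t-test n divided by the worst-case Mann-Whitney efficiency: 8.06/0.864 = 9.33, so 10 per arm.

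The test behind the calculation is not named. The stated ten is within one per arm of the t-test answer and slightly conservative. The figure is not in dispute.

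**3. Power after losses.** Two-sided t-test, alpha 0.05, noncentrality 1.5 × √(n/2), degrees of freedom 2n − 2:

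| Analysed per arm | Noncentrality | Power |
|---|---|---|
| 10 | 3.35 | 88.7% |
| 9 | 3.18 | 84.8% |
| 8 | 3.00 | 79.7% |
| 7 | 2.81 | 73.1% |

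With unequal losses, 10 against 7 gives 81.2% and 9 against 7 gives 79.0%. Power stays near the 80% target until about 4 of the 20 are lost.

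**4. How likely a loss is.** The documents give no loss rate, so 5%, 10% and 20% before T1 are assumptions. The chance of at least one loss among 20 is 1 − (1 − p)²⁰:
- 5%: 64%
- 10%: 88%
- 20%: 99%

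If randomisation stayed at Screening, keeping ten per arm would need 10/(1 − p) randomised per arm:
- 5%: 10.5, so 11
- 10%: 11.1, so 12
- 20%: 12.5, so 13

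**5. Outer bound on bias.** By simulation with no true effect, the 1, 2 or 3 patients with the worst outcomes out of 10 were removed from one arm only. The difference shifts by 0.17, 0.32 or 0.46 SD, and two-sided type I error rises from 5% to about 7%, 11% or 17%. This is a deliberately extreme case; the documents show no mechanism that would produce it.

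**The case against.** The strongest reply is that losses before V1 have no documented route to depend on the arm. No stimulation has been given, the comparison is sham-controlled, and the assessor and raters are blinded. Losses unrelated to the arm cost precision and do not bias the comparison. This stands.

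A reader might infer that the TMS physician knows the arm while the V1 date is being chosen, so that T1 timing will differ between arms. The documents do not support this. They say the physician is aware of the arm, not when that knowledge arrives, nor that the physician books the visit. What can be said is that concealment up to V1 is not described.

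A reader might also infer that a patient lost before V1 cannot be replaced. That goes too far. Further patients could be randomised until ten per arm complete, given a rule for the analysis set; the plan simply has no such rule.

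Nor should 8 weeks be read as a stated interval. It is the outer edge of the BoNT-to-rTMS window, and it applies only when rTMS follows BoNT.

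Finally, the power figures are reassuring: two losses per arm leave the plan at about its 80% target. What survives is that early randomisation has no benefit visible in the schedule, that losses in the gap become unplanned exclusions, and that an avoidable opening for allocation to affect T1 is left in place.

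**Conclusion.** The point holds as a cheap improvement. It does not show that the comparison is invalid. The expected cost is mainly precision: one loss per arm takes power from 88.7% to 84.8%, two to 79.7% and three to 73.1%. This assumes the plan's own 30% difference and 20% SD, and a simple t-test standing in for the mixed model. Bias is conditional on someone who knows the allocation influencing when T1 happens or who reaches it. The plan leaves that possible because one physician is unblinded and no concealment until V1 is described, but nothing in it shows that this would occur. The 2-8 week gap rests on reading randomisation and BoNT as close in time, with rTMS afterwards.

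**What to change.** In the Time and Events Table, move the randomisation mark from Screening to rTMS V1. State in Study Design that the arm is assigned once the T1 video, TWSTRS, CBI and pre-rTMS MRI are complete, and immediately before the first session. Patients lost before V1 are then screen failures who can be replaced. Every randomised patient has a T1 baseline recorded before the allocation exists, and the allocation can no longer affect the T1 date.

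Reconcile the table, which shows BoNT before rTMS, with the text, which allows either order, so that the interval between Screening and V1 is defined in every case.

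The cost is one table cell and a sentence of text, with no extra patients, visits or assessments. The downside is practical: real or sham must be set up on the day of V1, after all T1 assessments are finished.

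This does not deal with losses after V1. Nor does it change the optional status of the 10- and 12-week visits, the first of which carries the outcome used in the power calculation.
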